Genetic (DNA) evaluation (where local regulations permit)		X																	Whole blood will be collected only from participants who consent to participate in the optional DNA analysis. The pharmacogenomic (DNA) sample should be collected at the specified time point; however, if necessary it may be collected later without constituting a protocol deviation.
Efficacy (clinical as	ssessments/C	D-re	lated	healt	hcare	utili	zation	/PRC	Os)										
Electronic daily diary by site staff		x	х	х	х	х	х	x	x	x	x	х	х	х	х		х	х	Remind participant to complete electronic daily diary for the length of the study. The daily diary includes patient-reported data for the CDAI (includes PRO-2 components).

Study Procedure	Screening Visit (within 5 weeks prior to Week 0)								Stu	dy vis	sits (V	Veek)ª	1				Flare visit a,c	Early Termination visit ^{a,d}	Notes
		0	8	16	24	32	40	48	64	80	96	112	128	144 Final dose	152 Final efficacy	156 Final safety			
CDAI assessments		x	x	х	x	x	х	x	x	x	x	X	Х	X	X		X	X	For calculation of CDAI. The hematocrit value obtained during screening will be used to calculate CDAI at Week 0. For all other visits, the hematocrit value from the most recent study visit available will be used to calculate the CDAI.
Weight (component of CDAI)	Х	X	X	х	х	X	x	X	X	x	x	х	Х	х	Х		X	х	In kilograms (kg)
Fistula assessment	X	X	X	X	X	X	X	X	X	X	X	X	X	X	X		X	X	

Study Procedure	Screening Visit (within 5 weeks prior to Week 0)								Stu	dy vis	sits (V	Veek) ^a	ı				Flare visit	Early Termination visit ^{a,d}	Notes
		0	8	16	24	32	40	48	64	80	96	112	128	144 Final dose	152 Final efficacy	156 Final safety			
Video ileocolonoscopy with biopsy and histology					Xf			X^{f}							X f		X	X f	Week 24 procedure is optional, at the discretion of the investigator with agreement of the participant and should be performed ± 14 days from the scheduled visits. Week 48 procedure should be performed between Weeks 48 to Week 51. In the event procedure performed on the day of the designated visit or the 7 days prior, CDAI scores should be calculated using the proximate 7 days that were not impacted by the ileocolonoscopy or its preparation. Refer to the biopsy manual for details on the biopsy sample collection.
Stool sample (fecal calprotectin)	х	х			х		х	х		х			х		х		х		Week 0: Not required if sample already collected during screening is within 2 weeks of the Week 0 visit.

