Study agent administration should not occur when a participant is experiencing a clinically important, active infection, an example of an appropriate reason to deviate from protocol-specified windows (which should then be documented appropriately).

The participant will be instructed to complete the CDAI daily diary through Week 152. For all visits where a score needs to be calculated in real-time, the most recent hematocrit value available will be used when calculating the CDAI score.

Flare Visit

During the study, participants who are suspected to be having a flare of disease activity (eg, example, an increase in the PRO-2 [as described in Section 8.1.2] score of at least 50 points over a 7-day period compared to baseline, or suspicion of a new fistula or abscess) can present for further evaluation at the flare visit (see SoA). This visit may include an endoscopy if it is determined that participant has a both a CDAI score of over 200 and an increase of at least 70 points over baseline.

Participants in clinical flare should undergo endoscopy, unless it can be determined without endoscopy that they have met criteria for disease recurrence (see Section 9.4.3).

Cross Over Visit

After Week 8, if a determination has been made that the participant has had a disease recurrence (by meeting the criteria outlined in Section 9.4.3 and confirmed by the central reader of i2a or greater disease when applicable) a cross over visit should be scheduled. Participants who have endoscopic recurrence confirmed by the central reader at the scheduled Week 48 ileocolonoscopy or on a flare visit ileocolonoscopy will be scheduled for a cross over visit. In addition, participants who are determined by the central reader to have endoscopic recurrence at the Week 24 (but do not have disease recurrence) can also schedule a cross over visit at the discretion of the principal investigator.

Procedures to be performed at the cross over visits are outlined in the Cross Over SoA (Section 1.3). Participants will receive their first dose of open-label guselkumab 400 mg SC at the cross over visit. Participants will then get a second dose4 weeks after the cross over visit which will be self-administered at home. The third dose will be given 8 weeks after the

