5.4.1.3. Analysis Methods

The analyses of the secondary endpoints will be based on the Full Analysis Set (FAS), which includes all randomized participants. Participants will be analyzed according to the intervention group to which they were randomized regardless of the study intervention they actually received.

Estimators of Clinical Remission at Week 48 without Disease Recurrence

Summaries of the proportion of participants that achieve clinical remission without disease recurrence by treatment group will be provided. To compare the guselkumab versus placebo group for the first secondary endpoint, the CMH chi-square test (2-sided) will be used with stratification of clinical remission status at baseline (CDAI < 150, CDAI \ge 150), region (North America, Western Europe, rest of world) and number of prior surgeries (1 surgery versus > 1 surgery, with the qualifying surgery counting as 1 surgery).

After accounting for the ICE strategies, missing data will be imputed by multiple imputation. Multiple imputation will be used for imputing missing data under the assumption that the data are MAR. The analysis will impute the missing Rutgeerts score at Week 48 using the analysis method and ancillary variables as described in Table 11. The responses at Weeks 48 will be derived from the imputed datasets and combined for analysis.

Variable	MI specification	Analysis method/Summary statistics
CDAI score at Week 48	Multiple imputation with monotone regression of total scores	 MIdataset1 (N=200, Seed=5748941) Imputation variables: CDAI at Week 48 Ancillary variables: Treatment group, baseline Rutgeerts score, history of primary non-response to at least one approved ADT (Yes, No), clinical remission status at baseline (CDAI < 150, CDAI ≥ 150), region (North America, Western Europe, rest of world) and number of prior surgeries (1 surgery versus > 1 surgery, with the qualifying surgery counting as 1 surgery)

Table 11:Multiple Imputation Methods for CDAI at Weeks 48

Estimators of Disease Recurrence

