Summaries of median survival time and interquartile range of survival time by treatment group will be provided. The log-rank test will be used to compare disease recurrence distribution between the two treatment groups. The Kaplan-Meier method will be used to estimate the distribution of disease recurrence for each treatment. The treatment effect (hazard ratio) and its two-sided 95% confidence intervals are to be estimated using Cox regression model with treatment and stratification factors. Participants who have not achieved disease recurrence during the main study period at the database lock will be censored at the last visit. Participants without any post-baseline follow-up will be censored at randomization.

Estimators of Abdominal Pain Free at Week 48

Summaries of the proportion of participants that achieve abdominal pain free by treatment group will be provided. To compare the guselkumab versus placebo group for the first secondary endpoint, the CMH chi-square test (2-sided) will be used with stratification of clinical remission status at baseline (CDAI < 150, CDAI \ge 150), region (North America, Western Europe, rest of world) and number of prior surgeries (1 surgery versus > 1 surgery, with the qualifying surgery counting as 1 surgery).

After accounting for the ICE strategies, missing data will be imputed by multiple imputation. Multiple imputation will be used for imputing missing data under the assumption that the data are MAR. The analysis will impute the missing Rutgeerts score at Week 48 using the analysis method and ancillary variables as described in Table 12. The responses at Weeks 48 will be derived from the imputed datasets and combined for analysis.

Variable	MI specification	Analysis method/Summary statistics
AP score at Week 48	Multiple imputation with monotone regression of total scores	 MIdataset1 (N=200, Seed=5748941) Imputation variables: AP score at Week 48 Ancillary variables: Treatment group, baseline Rutgeerts score, history of primary non-response to at least one approved ADT (Yes, No), clinical remission status at baseline (CDAI < 150, CDAI ≥ 150), region (North America, Western Europe, rest of world) and number of prior surgeries (1 surgery versus > 1 surgery, with the qualifying surgery counting as 1 surgery)

Table 12:	Multiple Imputation Methods for AP Score at Weeks 48
-----------	--

Estimators of Recurrence of Symptoms

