Summaries of median survival time and interquartile range of survival time by treatment group will be provided. The log-rank test will be used to compare disease recurrence distribution between the two treatment groups. The Kaplan-Meier method will be used to estimate the distribution of disease recurrence for each treatment. The treatment effect (hazard ratio) and its two-sided 95% confidence intervals are to be estimated using Cox regression model with treatment and stratification factors. Participants who have not achieved disease recurrence during the main study period at the database lock will be censored at the last visit. Participants without any post-baseline follow-up will be censored at randomization.

Estimators of Steroid Free Clinical Remission at Week 48

Summaries of the proportion of participants that achieve steroid free clinical remission by treatment group will be provided. To compare the guselkumab versus placebo group for the first secondary endpoint, the CMH chi-square test (2-sided) will be used with stratification of clinical remission status at baseline (CDAI < 150, CDAI \ge 150), region (North America, Western Europe, rest of world) and number of prior surgeries (1 surgery versus > 1 surgery, with the qualifying surgery counting as 1 surgery).

After accounting for the ICE strategies, missing data will be imputed by multiple imputation. Multiple imputation will be used for imputing missing data under the assumption that the data are MAR. The analysis will impute the missing Rutgeerts score at Week 48 using the analysis method and ancillary variables as described in Table 13. The responses at Weeks 48 will be derived from the imputed datasets and combined for analysis.

Variable	MI specification	Analysis method/Summary statistics
CDAI score at Week 48	Multiple imputation with monotone regression of total scores	 MIdataset1 (N=200, Seed=5748941) Imputation variables: CDAI at Week 48 Ancillary variables: Treatment group, baseline Rutgeerts score, history of primary non-response to at least one approved ADT (Yes, No), clinical remission status at baseline (CDAI < 150, CDAI ≥ 150), region (North America, Western Europe, rest of world) and number of prior surgeries (1 surgery versus > 1 surgery, with the qualifying surgery counting as 1 surgery)

 Table 13:
 Multiple Imputation Methods for CDAI at Weeks 48

Type I error will be controlled over the primary and secondary endpoints hierarchically. The sequence of tests will be:

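### The imputation models for Week 48 CDAI and abdominal pain use no post-baseline symptom values, so values still missing after intercurrent-event handling are imputed without the participant's own course

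*SAP*

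**What the plan says.** SAP Section 5.4.1.3 applies multiple imputation to three secondary endpoints, at positions 2, 4 and 6 of the testing hierarchy. The stated basis is: "Multiple imputation will be used for imputing missing data under the assumption that the data are MAR".

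- Table 11 (clinical remission without disease recurrence): "Imputation variables: CDAI at Week 48 Ancillary variables: Treatment group, baseline Rutgeerts score, history of primary non-response to at least one approved ADT".
- Table 12 (abdominal pain free): "Imputation variables: AP score at Week 48 Ancillary variables: Treatment group, baseline Rutgeerts score, history of primary non-response to at least one approved ADT".
- Table 13 (steroid-free clinical remission): "Imputation variables: CDAI at Week 48 Ancillary variables: Treatment group, baseline Rutgeerts score", and otherwise the same list as Table 11.

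Each list ends with the three stratification factors: baseline CDAI category (below 150, or 150 and above), region and number of prior surgeries. The method named is monotone regression, but only one visit's score is in the model.

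The trial collects far more. The Protocol's Schedule of Activities (Section 1.3) has CDAI at Weeks 0, 8, 16, 24, 32, 40 and 48. On the diary it states: "The daily diary includes patient-reported data for the CDAI (includes PRO-2 components". Protocol Section 8 adds: "The participant will be instructed to complete the CDAI daily diary through Week 152".

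Imputation comes after the ICE rules. Under SAP Table 9 and Appendix 9, four kinds of event count as failure before any imputation:

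- CD-related surgery
- a prohibited CD medication change, including oral steroids started for worsening CD
- discontinuation for lack of efficacy or an AE of worsening CD
- cross over to open-label guselkumab

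Discontinuation for other reasons (ICEs 5 and 6) is treatment policy: observed data are used if available, and missing values are imputed.

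**The concern.** Dropout that depends on recent symptoms is missing at random only if those symptoms are in the imputation model. Here they are not. Two participants in the same arm with the same baseline category, region, surgery count and ADT history get draws from the same distribution, even if one had a CDAI of 80 at Week 40 and the other 230.

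If the sicker participant is more likely to have no Week 48 value, imputed remission is too high. If that tendency differs between arms, the treatment difference is biased. Without bias, precision is still lost.

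No planned check would show this. The tipping point analysis (SAP Section 5.3.5.1) covers the primary endpoint only. The SAP also treats its uncontrolled continuous endpoints better: Section 5.5.2 analyses them with an MMRM that uses the correlation between visits.

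**Working it through.** **1. The plan's own figure.** Protocol Table 6 gives 95.4% power for 20% v 37% with 185 per arm and two-sided alpha 0.05. With pooled variance under the null:

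- mean rate = (0.20 + 0.37)/2 = 0.285
- null SE = √(2 × 0.285 × 0.715/185) = 0.0469
- alternative SE = √((0.20 × 0.80 + 0.37 × 0.63)/185) = 0.0461
- z = (0.17 − 1.96 × 0.0469)/0.0461 = 1.69, so power is 95.5%

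The figure reproduces. It assumes complete data, so the imputation model does not change it.

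**2. How much may be missing.** The documents give one dropout rate, 15% a year, stated for the time-to-event power. By Week 48 that is 1 − 0.85^(48/52) = 13.9%, from all causes and before ICE 1-4 cases are taken out.

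**3. Which worsening participants still reach imputation.**

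- Someone who meets the CDAI recurrence criteria without endoscopic confirmation stays on assigned treatment (Protocol 6.5.1). Stopping later for another reason is ICE 6.
- A CDAI of 150 to 199 fails remission but is below the 200 needed for CDAI-based recurrence.
- Any AP above 0 fails the pain-free endpoint, yet mild pain triggers no ICE.
- After stopping treatment, participants are followed for about 12 weeks (Protocol 7.1). An ICE 6 stop before about Week 36 (48 − 12) therefore tends to leave no Week 48 value, although interim values exist.

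**4. One participant (assumed inputs).** Take a placebo mean of 150, SD 70, and Week 40 to Week 48 correlation ρ. A participant 1 SD above the mean at Week 40 has CDAI 220. The Week 48 expectation is 150 + 70ρ, with SD 70√(1 − ρ²).

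- ρ = 0.5: mean 185, SD 60.6, P(CDAI < 150) = Φ(−35/60.6) = 0.28
- ρ = 0.7: mean 199, SD 50.0, P = Φ(−49/50.0) = 0.16

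Ignoring Week 40, and before any baseline-category adjustment, the probability is Φ(0) = 0.50.

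**5. Large-sample simulation, no ICE rule.** Assumed: arm means 120 (guselkumab) and 150 (placebo), SD 70, dropout rising with Week 40 CDAI. The SAP-type model uses arm and baseline category; the comparison adds Week 40 CDAI.

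| Scenario | True | SAP-type | With Week 40 |
|---|---|---|---|
| Placebo dropouts at least 1 SD above mean: P(remission) | 0.06-0.20 | 0.47-0.51 | 0.06-0.20 |
| Guselkumab rate, ρ 0.5, 5% missing, weaker dependence | 0.671 | 0.677 | 0.671 |
| Guselkumab rate, ρ 0.7, 13.9% missing, stronger dependence | 0.673 | 0.709 | 0.673 |
| Placebo rate, same stronger setting | 0.508 | 0.543 | 0.507 |
| Difference, same stronger setting | 0.165 | 0.166 | 0.166 |
| Difference, ρ 0.7, missing 5% guselkumab, 15% placebo | 0.166 | 0.141 | 0.166 |
| Difference, ρ 0.7, missing 15% guselkumab, 5% placebo | 0.166 | 0.192 | 0.166 |

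Arm rates are overstated by 0.6 to 3.6 points. The difference shifts by −2.5 or +2.6 points with unequal dropout; with ρ = 0.5 the shifts are −1.9 and +1.7.

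**6. Allowing for ICEs 1-4.** A second simulation used 185 per arm, random intercept SD 45, slope SD 0.8 per week, residual SD 30, logit dropout per visit −5.3 + 0.014 × CDAI, and an assumed CDAI course. The share of dropouts with last CDAI at least 150 that counts as ICE non-response is also assumed.

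| Share | Arm overstatement, dropout in both arms | Bias in difference, symptom-driven dropout in one arm only (absolute) |
|---|---|---|
| 0% | about 3 points | 2.5 to 3.2 points |
| 50% | about 1.5 points | about 2 points |
| 80% | about 0.6 points | 1.3 to 1.4 points |

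With symptom-driven dropout in both arms, the bias in the difference is 0.1 to 0.3 points.

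**The case against.** The strongest defence is that the ICE rules remove most of the participants who would cause trouble. Stopping for lack of efficacy or worsening CD, starting steroids or immunomodulators for worsening CD, surgery and cross over all count as failure before imputation, and disease recurrence fails the first secondary endpoint directly. This stands, and it reduces the effect materially, as step 6 shows. It does not close the routes in step 3.

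A reader might infer three stronger things that the documents do not support.

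- **That baseline CDAI is ignored.** It enters as a two-level factor. What is lost is the continuous value.
- **That anyone worsening before dropout is imputed as an average arm member.** Many are never imputed, and the rest are drawn within arm and covariate category.
- **That the treatment difference is biased by 3.5 to 4.5 points.** Figures of −3.5 and +4.5 arise if symptoms drive dropout in one arm and have no effect in the other, with no ICE rule applied. That is an extreme assumption for a double-blind trial.

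The simulations also model CDAI remission alone. The first secondary endpoint further requires no endoscopic recurrence and no disease recurrence, so a wrong CDAI draw matters only for participants who otherwise qualify. AP was not simulated.

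**Conclusion.** The omission is plain in Tables 11-13, and it makes the MAR assumption weaker than it need be for three confirmatory endpoints. Its likely size is modest: roughly 0.5 to 4 points of overstated remission per arm, almost nothing on the difference when dropout is similar in both arms, and about 1 to 3 points in either direction when it differs. Direction and mechanism are secure. The sizes rest on assumed CDAI courses, correlations, dropout models and ICE shares, none of which the documents give, and for AP the argument is by analogy only.

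This is a worthwhile improvement rather than a flaw that undermines the trial. SAP Section 1 reports that four participants were enrolled and that the planned analyses no longer apply, so the point matters for the plan as written and for any reuse of its text.

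**What to change.** - **Tables 11 and 13:** impute CDAI sequentially through Weeks 8, 16, 24, 32, 40 and 48, with continuous baseline CDAI, arm and the stratification factors as predictors. Use fully conditional specification for intermittent gaps.
- **Table 12:** do the same with baseline and interim mean AP. Use predictive mean matching, or a logistic model for AP = 0, because an ordinary regression draw will not equal exactly 0.
- **All three:** exclude values recorded after an ICE 1-4, including those after cross over, from the imputation model. Derive responder status from the completed Week 48 value after the ICE rules are applied.

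The cost is revised table wording and somewhat more programming. No new data, visits or participants are needed.

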The CDAI diary will be completed by participants during the screening period. The investigator or appropriate site personnel will use the hematocrit value obtained during screening to calculate the CDAI score at Week 0.

A minimum of 7 days of CDAI data during the screening period is required to calculate the CDAI score at baseline (Week 0).

Women of childbearing potential must have a negative serum pregnancy test result at screening. Participants must be reminded that they are required to use a highly effective method of contraception during the study (as described in Inclusion Criterion 11) and must continue taking such precautions for 12 weeks after receiving the last administration of study intervention. The method(s) of contraception used by each participant must be documented.

The 'Baseline/Screening' version of the C-SSRS will be conducted during the screening visit and the 'Since Last Visit' version of the C-SSRS will be completed at Week 0.

Participants must undergo testing for TB (Section 8.4.9.1) and their medical history assessment must include specific questions about a history of TB or known occupational or other personal exposure to individuals with active TB. The participant should be asked about past testing for TB, including chest radiograph results and responses to tuberculin skin or other TB testing. A participant's eligibility according to TB screening criteria is described in Section 5.2, Exclusion Criteria.

Week 0 Visit

Prior to entering the study, the participant must be evaluated for eligibility.

An assessment of all previous laboratory results, clinical data, and concomitant medication data will be made by the principal investigator or designee to confirm that the participant satisfies all inclusion criteria and does not violate any exclusion criteria prior to randomization.

Post-baseline Visits

Study visits should occur at the week indicated \pm 10 days. Note that while out of window visits should be recorded as protocol deviations, it is preferable to perform visits and procedures out of window than not perform them at all. One exception may be if sufficient time has passed that it is now in-window for the next subsequent visit, in which case it is advised to contact the medical monitor for assistance in how to best manage the situation.

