1. INTRODUCTION

A Randomized, Double-blind, Placebo-controlled Study Evaluating the Safety and Efficacy of Guselkumab for the Treatment of Participants with Crohn's Disease After Surgical Resection: PROGRESS

Janssen made an internal business decision to discontinue the PROGRESS study. This decision is not related to any efficacy or safety concerns. Only four subjects were enrolled, and the originally planned statistical analyses are no longer applicable.

We will report data collected on those four patients including:

- Baseline characteristics: demographics, medical history of interest, date of CD diagnosis, Montreal classification, prior gastrointestinal surgeries, prior CD medications, qualifying surgery information, corticosteroid use
- Efficacy assessments: Rutgeerts score, CDAI score, fistula assessment, fecal calprotectin, CRP, medical resource utilization
- Safety assessments: adverse events, concomitant and prohibited medications, hematology, clinical chemistry
- Pharmacokinetics and immunogenicity: serum guselkumab concentration, antibody status (titer and neutralizing antibodies status)

Below are the originally planned statistical analyses for reference.

This SAP contains definitions of the analysis sets, derived variables, and statistical methods for all planned analyses for the main study period database lock and the Week 156 database lock. The term "study intervention" throughout this SAP refers to placebo and guselkumab.

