4. POPULATIONS (ANALYSIS SETS) FOR ANALYSIS

5. STATISTICAL ANALYSES

5.1. General Considerations

- Unless otherwise specified, for each study, data from all investigational centers/sites will be pooled for analysis
- Study Day 1 refers to the day of the first study intervention administration. All efficacy and safety assessments at all visits will be assigned a day relative to this day.

Study day for a visit is defined as:

- Visit date (date of Study Day 1) +1, if visit date is \geq date of Study Day 1
- Visit date date of Study Day 1, if visit date < date of Study Day 1

There is no 'Study Day 0'.

- Baseline assessment is defined as the last available assessment collected prior to the first study intervention.
- Descriptive statistics (ie, N, mean, median, SD, IQ range, minimum and maximum) will be used to summarize continuous variables. Counts and percentages will be used to summarize categorical variables. Graphical data displays (eg, line plots) may also be used to summarize the data.

CONFIDENTIAL – FOIA Exemptions Apply in U.S.

- The following conventions will be applied for reporting descriptive statistics of all continuous parameters. For presentation, the mean and median will be presented to 1 decimal greater than the original data, SD will be 2 decimal places greater than the original data, and the minimum and maximum will have the same number of decimal places as the original data.
- The following intervention groups will be presented through Week 48, unless otherwise stated:
 - Placebo
 - Guselkumab

Partial dates for adverse events will be imputed as described in Appendix 11.

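### The imputation models for three alpha-controlled secondary endpoints call for a baseline Rutgeerts score that the trial never measures

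*SAP*

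**What the plan says.** **Status.** SAP Section 1 says: "Only four subjects were enrolled, and the originally planned statistical analyses are no longer applicable". The planned analyses remain in the document for reference.

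**Imputation models.** SAP Section 5.4.1.3 imputes missing Week 48 data by monotone regression under missing at random. Table 11 (clinical remission without disease recurrence), Table 12 (abdominal pain free) and Table 13 (steroid-free clinical remission) all give the ancillary variables as "Treatment group, baseline Rutgeerts score, history of primary non-response to at least one approved ADT", followed by baseline remission status, region and number of prior surgeries.

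**Baseline and endoscopy.** SAP Section 5.1 states: "Baseline assessment is defined as the last available assessment collected prior to the first study intervention". The earliest mark in the ileocolonoscopy row of the Protocol's Schedule of Activities (Section 1.3) is Week 24, with the note "Week 24 procedure is optional, at the discretion of the investigator with agreement of the participant".

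**What is imputed.** The sentence above Table 11 reads "The analysis will impute the missing Rutgeerts score at Week 48 using the analysis method and ancillary variables as described in Table 11". Those above Tables 12 and 13 ("The analysis will impute the missing Rutgeerts score at Week 48 using the analysis method and ancillary variables as described in Table 12" and "The analysis will impute the missing Rutgeerts score at Week 48 using the analysis method and ancillary variables as described in Table 13") differ only in the table number. The tables themselves impute CDAI, AP score and CDAI.

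**Intercurrent events.** In SAP Sections 5.4.1.2.1, 5.4.1.2.3 and 5.4.1.2.5, the variable is the favourable outcome *or* having an intercurrent event (ICE) in categories 1-4. Protocol Section 9.4.3 does the same for the first of these endpoints. SAP Table 9 classes participants with those events as not achieving the endpoint.

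**The concern.** A regression imputation model needs observed values of its predictors. If one predictor is never collected, the analyst has to drop it, invent a value or change the model. Any of these is a decision taken outside the pre-specified plan. Three of the six tests under type I error control are affected.

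The mismatch between sentences and tables adds to this. Clinical remission without disease recurrence depends on both Week 48 CDAI and endoscopic status by Week 48. Table 11 covers only CDAI, and Section 5.4.1.3 never refers to Table 8, where imputation of the Rutgeerts score is specified.

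The *or* in the variable definitions suits the primary endpoint, where the event is unfavourable. Carried over to favourable endpoints and read literally, it would count CD-related surgery, a prohibited medication change or cross over as success.

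**Working it through.** **1. The plan's own figure.** Of the three endpoints, only clinical remission without disease recurrence has a stated power: 95.4% for 20% v 37% (Protocol Table 6). With 185 per arm, two-sided alpha 0.05 and pooled variance under the null:

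- mean rate = (0.20 + 0.37)/2 = 0.285
- null term = √(2 × 0.285 × 0.715) = 0.6384
- alternative term = √(0.20 × 0.80 + 0.37 × 0.63) = 0.6270
- z = (0.17 × √185 − 1.96 × 0.6384)/0.6270 = (2.3123 − 1.2512)/0.6270 = 1.692
- power = 95.5%

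This reproduces the stated value to within 0.1 point.

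**2. Is the predictor ever measured?** Matched to its visit columns, the ileocolonoscopy row is marked at:

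| Screening | Week 0 | Week 24 | Week 48 | Week 152 | Flare | Early termination |
|---|---|---|---|---|---|---|
| – | – | optional | yes | yes | yes | yes |

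The biopsy row is also empty before Week 24. Protocol Section 8.1.3 ties endoscopy to the Schedule of Activities. The score grades the neo-terminal ileum and anastomosis after resection, so a pre-operative endoscopy cannot supply it. Randomization falls at most 49 days after surgery, and no inclusion criterion asks for an endoscopy in that interval. SAP Table 8, which imputes the Week 48 Rutgeerts score itself, does not list a baseline value.

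**3. Can the models be fitted?** Three cases were tried with 370 rows of arbitrary covariate values:

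- Predictor missing for everyone: 0 of 370 rows have complete covariates, so nothing can be estimated.
- Everyone assumed to be i0: the column is constant. The design has 8 columns and rank 7, so its coefficient is not identified.
- Term deleted: intercept, treatment, history of non-response, remission status, two region indicators and prior surgeries give 1 + 1 + 1 + 1 + 2 + 1 = 7 columns, rank 7. The model can be fitted.

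**4. Sentence against table.**

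| Table | Endpoint (test) | Sentence names | Table imputes | Week 48 quantities needed |
|---|---|---|---|---|
| 11 | Clinical remission without disease recurrence (2) | Rutgeerts | CDAI | CDAI and Rutgeerts |
| 12 | Abdominal pain free (4) | Rutgeerts | AP score | AP score |
| 13 | Steroid-free clinical remission (6) | Rutgeerts | CDAI | CDAI and steroid use |

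**5. How many participants would depend on the model?** The documents give no rate of missing Week 48 data. Assume 5% to 20%; the 15% row borrows the annual dropout stated for the time-to-event calculation. The number to impute is 370 × the missing share. Available-case power repeats step 1 with n = 185 × (1 − share).

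| Missing | To impute | n per arm | Available-case power |
|---|---|---|---|
| 5% | 18.5 (about 19) | 175.75 | 94.5% |
| 10% | 37 | 166.5 | 93.4% |
| 15% | 55.5 (about 56) | 157.25 | 92.0% |
| 20% | 74 | 148 | 90.4% |

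**The case against.** The strongest reply is that nothing will go wrong in practice. No imputation or hierarchy will be run on four participants. Had the trial continued, a blinded correction before the first database lock would have been simple. Once the unmeasured term is struck out, the remaining predictors match Table 8 exactly, with the same method, number of imputations and seed, so a natural fallback already exists. All of this stands and bears on how serious the fault is. It does not make Tables 11 to 13 executable as written, and the SAP nowhere tells the analyst to use that fallback.

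The lesser points draw fair replies too:

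- For Table 11, the sentence and the table could be read together as imputing both quantities, and Tables 8 and 11 share a dataset label. That reading is possible but not stated. For Tables 12 and 13 the mismatch is plain.
- On intercurrent events, Table 9 and the surrounding text make the intent clear, and a sensible analyst would follow them. The variable lines still say the opposite.
- The power figures in step 5 show the effect of a smaller sample, not of an unmeasured covariate. This is correct. The counts are also upper bounds, because participants already classified as failures through ICEs 1-4, or through one observed failed component, need no imputation.
- Table 15 lists no baseline Rutgeerts score, but it does list IBDQ, which is not among the Protocol's efficacy assessments. It is therefore a weak inventory of what is measured. The Schedule of Activities settles the matter without it.

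**Conclusion.** The concern holds. As issued, the missing-data models for tests 2, 4 and 6 of six cannot be fitted, because a named predictor is unmeasured for 370 of 370 planned participants. A site might hold an incidental post-operative endoscopy, but it would be neither scheduled nor centrally read and could not supply the covariate for the Full Analysis Set.

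The sentences naming the imputed variable and the *or* in the variable definitions are real contradictions of lesser weight.

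No stated power changes. Under the assumed 5% to 20% missingness, about 19 to 74 participants at most would depend on the imputation, and available-case power for the first secondary endpoint would stay between 94.5% and 90.4%. The fault is a specification that cannot be executed and contradicts itself, not lost power. It should be fixed in the plan as designed; it has no effect on the four participants to be reported.

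**What to change.** - **Predictors.** Delete the baseline Rutgeerts score from Tables 11, 12 and 13. This alone makes the models estimable. Preferably, put continuous baseline CDAI in Tables 11 and 13 and baseline AP score in Table 12. Both come from the screening diary, for which Protocol Section 8 already requires at least 7 days of data. Continuous CDAI overlaps with the dichotomised remission status already in the model, so it refines the model and is not needed to fit it.
- **Imputed variable.** Correct the three introductory sentences to name CDAI, AP score and CDAI. For clinical remission without disease recurrence, state that Week 48 CDAI and Week 48 Rutgeerts score are both imputed, and refer to Table 8 for the latter.
- **Variable definitions.** In SAP Sections 5.4.1.2.1, 5.4.1.2.3 and 5.4.1.2.5, and in Protocol Section 9.4.3 for the first endpoint, require the favourable outcome *and* the absence of ICEs 1-4.

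The cost is wording in three tables, three sentences, three SAP definitions and one Protocol line. No new data, visits or procedures are needed.
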